#### **15.1** Adverse Events

#### Definitions

The recording period for AEs begins when the patient is initially included in the study (date of signature of first informed consent) and continues at least to the end of the mandatory safety follow-up period (i.e., up to 24 months in most patients or up to 30 months in patients with delayed start of Year 2 treatment).

TEAEs: those AEs with onset dates occurring within the treatment period (that is after the first dose and until the end of the follow-up period).

For the analyses, ADRs will be those TEAEs reported in the eCRFs as related to study treatment or those AEs where such a relationship is missing.

All analyses described in Section 15.1 will be based on TEAEs if not otherwise specified.

Event rates (per patient-year of time on the study) will be calculated as the total number of events divided by the total time on study.

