¹ Life threatening in this context refers to a reaction in which the patient was at risk of death at the time of the reaction; it does not refer to a reaction that hypothetically might have caused death if more severe.

 2 Medical and scientific judgment should be exercised in deciding whether other situations should be considered as serious reactions, such as important medical events that might not be immediately life threatening or result in death or hospitalization but might jeopardize the patient or might require an intervention to prevent one of the other outcomes listed above. Such important medical events should be considered as serious.

Examples of such events are intensive treatment in an emergency room or at home for allergic bronchospasm, blood dyscrasias or convulsions that do not result in hospitalization or development of dependency or abuse. As a guidance, the important medical event terms list is intended to be used for assessment of suspected ADRs (see EMA/207865/2017).

Any suspected transmission via a medicinal product of an infectious agent is also considered a serious ADR.

Adverse Events of Special Interest

An adverse events of special interest (AESI) is an AE of scientific and medical concern specific to the Sponsor's product or program, for which ongoing monitoring and rapid communication by the investigator to the Sponsor can be appropriate. AESIs for monitoring should then be collected following the procedure for an SAE described in Section 11.4. The following events will be considered AESIs:

- Severe lymphopenia: defined as Grade 3 (<500 to 200 cells per microliter) or Grade 4 (<200 cells per microliter)
- Severe infection
- Tuberculosis
- Herpes zoster infection
- Progressive multifocal leukoencephalopathy
- Other opportunistic infection
- Malignancy

Events that Do Not Meet the Definition of a Serious Adverse Event

Elective hospitalizations (e.g. an overnight stay to facilitate therapy) are not considered as SAEs. However, all events leading to unplanned hospitalizations or unplanned prolongation of an elective hospitalization (e.g., undesirable effects of any administered treatment) must be documented and reported as SAEs.

Events Not to Be Considered an Adverse Event

Medical conditions present and documented at study start, that do not worsen in severity or frequency during the study are defined as baseline Medical Conditions and elective procedures and are NOT to be considered AEs.

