11.4 Recording of Adverse Events

The recording period for AEs begins when the patient is initially included in the study (date of signature of first informed consent) and continues at least to the end of the mandatory safety follow-up period (i.e. up to 24 months in most patients or up to 30 months in patients with delayed start of Year 2 treatment).

All safety data, as specified above, occurring during the study, must be documented by the investigator within 24 hours of awareness and recorded in the CRF, including its description, seriousness, severity (grading), duration (onset and resolution dates), causal relationship, any other potential causal factors, actions taken with the study drug (e.g. dose reduction, withdrawal), required treatment and outcome of the AE.

Note - Event term 'Death', 'Disability' and 'Hospitalization'

Death, disability, and hospitalization are considered outcomes in the context of safety reporting and not usually considered ADRs/AEs. Therefore, the primary cause of death, disability or hospitalization should be recorded and reported as an SAE/ADR, and the outcome should be recorded in a separate data field. However, a term for the outcome will be selected if it is the only information reported or provides significant clinical information.

If death occurs, the primary cause of death or event leading to death should be recorded and reported as an SAE. "Fatal" will be recorded as the outcome of this respective event and not be as separate event. Only if no cause of death can be reported (for example, sudden death, unexplained death), the death per se might then be reported as an SAE.

Reports of Special Situations (see definition in Section 11) are also to be recorded in the CRF following the AE procedure, even if occurring without AE.

Pregnancy and Breastfeeding. Pregnancy or breastfeeding must be recorded in the CRF and additionally be reported to the Sponsor immediately (within 24 hours of awareness) by using separate data collection forms for pregnancy, independent if an AE was reported or not (this includes male patients whose partner becomes pregnant during the cladribine treatment period). The outcome of the pregnancy should be followed up and reported to the Sponsor until delivery. In the event of a pregnancy occurring during the cladribine treatment period, the female patient must be discontinued from cladribine tablets immediately.

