To collect all serious adverse events (SAEs), adverse drug reactions (ADRs), adverse events of special interest (AESIs) and special situations during treatment with cladribine tablets over a 24-month period	SAEs, ADRs, AESIs	Adverse event (AE) collected from signed Informed Consent Form (ICF); Treatment- Emergent Adverse Events (TEAEs) considered after first treatment administration through the 24- month treatment period (or 30 months if Year 2 treatment is delayed)	Section 15
CCI			

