#### Missing data handling

Incomplete AE-related dates will be handled as follows:

- In case the onset date is missing completely or missing partially but the onset month and year, or the onset year are equal to the start of study dose then the onset date will be replaced by the minimum of the start of study dose and AE resolution date.
- In all other cases, the missing onset day or missing onset month will be replaced by 1.
- Incomplete stop dates will be replaced by the last day of the month (if day is missing only), if not resulting in a date later than the date of patient's death. In the latter case, the date of death will be used to impute the incomplete stop date.
- In all other cases, the incomplete stop date will not be imputed. If Stop date of AE is after the date of cutoff outcome of AE is ongoing at cutoff.

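### SAP 15.1 classes adverse events as treatment-emergent by onset date alone, so an event that starts between consent and first dose and then worsens on cladribine is not counted in the 15.1 outputs

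*SAP*

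**What the plan says.** - **TEAE definition.** The definitions in SAP 15.1 describe TEAEs as "those AEs with onset dates occurring within the treatment period (that is after the first dose and until the end of the follow-up period". The safety row of the table in SAP 5 has TEAEs "considered after first treatment administration through the 24- month treatment period" (or 30 months if Year 2 is delayed). Neither place mentions worsening.
- **Scope.** SAP 15.1 adds: "All analyses described in Section 15.1 will be based on TEAEs if not otherwise specified". That covers the overall frequency table, the table by system organ class and preferred term, and the AE listing in 15.1.1, and the discontinuation table in 15.1.2.
- **ADR definition.** In the same place, "ADRs will be those TEAEs reported in the eCRFs as related to study treatment or those AEs where such a relationship is missing".
- **Start of recording.** Protocol 11.4: "The recording period for AEs begins when the patient is initially included in the study (date of signature of first informed consent". Protocol 9.2.4 (Table 1) allows a screening visit from Day -45, and the text of that section expects some delay between the decision to treat and the first tablet.
- **Baseline conditions.** Protocol 11.1 does not treat as AEs those medical conditions documented at study start "that do not worsen in severity or frequency during the study are defined as baseline Medical Conditions". Worsening of MS itself goes to the relapse module unless it is suspected to be related to cladribine.
- **Imputed onsets.** Under missing data handling in SAP 15.1, an onset that is wholly missing, or partly missing but compatible with the month or year of first dose, is "replaced by the minimum of the start of study dose and AE resolution date".

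**The concern.** AEs with a pre-dose onset are expected in the database, because recording opens before treatment does. The protocol implies that a change for the worse matters, since it exempts baseline conditions only while they stay stable. The SAP's test looks at the onset date and nothing else. An event that is mild before the first dose and severe or serious after it is handled as if it had nothing to do with treatment.

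Collecting SAEs, ADRs and AESIs during cladribine treatment is a stated secondary objective (Protocol 8.2). The counts and rates that readers will use for it are the TEAE rows of SAP 15.1: any, serious, related, by severity, fatal, and leading to discontinuation or dose reduction. Where such a row holds only a few events, one misclassified patient is visible.

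**Working it through.** The documents give no figure to reproduce; the check is of the rules against each other.

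**Step 1. Apply the definition as written to each kind of record.**

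| Record | Meets the onset test? | Where it appears |
|---|---|---|
| AE starts between consent and first dose, worsens later, one record, not serious | No | Not in the 15.1.1 or 15.1.2 tables, nor in the 15.1.1 listing |
| Same, becomes serious | No | SAE listing in 15.2.2 only; 15.2.2 plans no frequency table |
| Same, fatal | No | Deaths table and listing in 15.2.1, but not the 15.1.1 row for TEAEs leading to death |
| Same start, but the worsening is entered as a new AE with its own date | Yes | All 15.1 outputs |
| Baseline condition that worsens after first dose, AE dated at the worsening | Yes | All 15.1 outputs |
| Baseline condition that worsens after first dose, AE dated at the condition's original onset | No | As rows 1 to 3 |
| Onset on the day of first dose | Depends on how *after* is programmed | 15.1 outputs only if the test is *on or after* |
| Uncertain onset imputed to the first-dose date | Same as the row above | Same as the row above |

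**Step 2. Ask which record the documents lead to.** Protocol 11.4 lists seriousness, severity, onset and resolution dates, and causality for each event. It names no date of worsening and does not say whether worsening opens a new record. Protocol 11.5 treats new information on a reported event as follow-up to that report. For an AE already open before dosing, this points towards one record with the pre-dose onset, without settling it. For a baseline condition, no AE exists until it worsens, so a post-dose onset date is the more natural entry; again nothing is stated.

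**Step 3. The first-dose date.** SAP 9 makes Day 1 the day dosing starts and defines no Day 0. With dates and no clock times, an onset on Day 1 equals the first-dose date and is not later than it. The imputation rule assigns uncertain onsets to exactly that date (unless the event resolved sooner). A literal *later than* test would discard the events the rule places there.

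**Step 4. Scale, for illustration only.**
- Full screening window against 24 months: 24 × 30.4375 = 730.5 days; 45 / 730.5 = 0.062, or 6.2%.
- Protocol 7.4 gives infection rates of 24.93 (cladribine 3.5 mg/kg) and 27.05 (placebo) adjusted AEs per 100 person-years. If either applied before dosing, infections starting in a full 45-day window would be 24.93 × 45 / 365.25 = 3.1 to 27.05 × 45 / 365.25 = 3.3 per 100 patients.
- Only those still open at first dose, later worse, and kept in one record would be lost. The documents give no rate for any of these three conditions and no overall AE rate, so the calculation stops here.

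**The case against.** The best reply is that the gap is narrow and the important events remain visible. Much of this stands.

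- **Other outputs.** The TEAE restriction covers Section 15.1 only. The deaths table and SAE listing in 15.2 are not limited to TEAEs, and 15.3 tabulates lymphopenia grades at each time point whatever the AE onset. A reader might infer that these events vanish from every safety output; they do not. What is lost is the count of a serious event and, for a non-serious event, its place in the AE tables and listing.
- **Baseline conditions.** A reader might infer that every worsened pre-existing condition is excluded. That would need entry under the original onset date, which no text requires. That worsening makes such a condition an AE is itself only implied by Protocol 11.1, and MS is expressly set apart.
- **Exposed window.** Forty-five days is the outer limit, the separate screening visit is optional, and the baseline visit comes just before treatment starts. Most patients may have a shorter interval.
- **Day 1.** The operative words refer to the treatment period, and the bracket explains them. The imputation rule makes sense only if the first-dose date counts as treatment-emergent. That is probably the intent, but the programmer still has to choose between > and ≥, and the literal text favours the wrong one.
- **ADR wording.** A pre-dose AE with no causality entry fits the second part of the ADR definition. The next sentence of SAP 15.1 and the table row that equates ADRs with related TEAEs mostly contain the slip.

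None of this supplies a worsening clause or a dating convention, so the first three rows of the table in the working remain.

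**Conclusion.** The point holds in a limited form. Followed as written, SAP 15.1 leaves out of its TEAE tables and listing an AE that starts between consent and first dose, worsens on cladribine and is kept as one record. That is a miscount produced by a stated rule. It rests on one assumption about data entry, that worsening updates the existing record; the documents neither confirm nor exclude this.

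The number of patients cannot be derived and is probably small, since an event must start in a short window, persist, worsen and stay in one record. A reader might also infer that all AE totals are shown to be biased low. The onset rule can only remove events from the TEAE counts, but the documents do not show that it removes any. For ADRs the missing-relationship wording pulls the other way, so even the direction is not fixed. The study is descriptive and single-arm, so no hypothesis test depends on this. It is still worth correcting because the AE counts and rates answer a stated objective and the remedy is cheap.

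**What to change.** In the SAP 15.1 definitions, replace the TEAE text with: *AEs with onset on or after the date of first dose and up to the end of follow-up, or AEs with earlier onset that worsen in severity or become serious on or after that date.* Identify the second group from the severity and seriousness data already collected. In the SAP 5 table, bring the TEAE timeframe into line. In the ADR definition, change the part on missing relationship from AEs to TEAEs.

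The cost is an edit to the SAP and a data-review check of AE records with a pre-dose onset that remain open after the first dose. As no date-of-worsening field is described, a few site queries may be needed, and these would have to be closed before database lock (planned for 3 June 2024 in Protocol 6). Worsening in frequency, which Protocol 11.1 also names, is not among the listed AE fields, so it is left out of the proposed text. TEAE counts may rise slightly.

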#### Missing data handling

Incomplete AE-related dates will be handled as follows:

- In case the onset date is missing completely or missing partially but the onset month and year, or the onset year are equal to the start of study dose then the onset date will be replaced by the minimum of the start of study dose and AE resolution date.
- In all other cases, the missing onset day or missing onset month will be replaced by 1.
- Incomplete stop dates will be replaced by the last day of the month (if day is missing only), if not resulting in a date later than the date of patient's death. In the latter case, the date of death will be used to impute the incomplete stop date.
- In all other cases, the incomplete stop date will not be imputed. If Stop date of AE is after the date of cutoff outcome of AE is ongoing at cutoff.

### 15.1.1 All Adverse Events

If an AE is reported for a given patient more than once during the study, the worst severity and the worst relationship to study drug will be tabulated.

The following overall frequency table will be prepared:

- Any TEAEs
- Treatment related TEAEs (ADRs)
- Any serious TEAEs
- Treatment related serious TEAEs
- Any TEAE by severity (Severe, Moderate, Mild)
- Treatment related TEAE by severity (Severe, Moderate, Mild)
- TEAEs leading to death
- Treatment related TEAEs leading to death.

The total number of TEAEs and rate (per patient-year of time on study) of TEAEs will be also reported.

A table showing the TEAE by Primary SOC and PT will be reported.

A listing with the following columns will be presented:

- Patient ID
- AE

- PT term
- Start/ End Date of AE
- Duration of AE (days)
- Relationship to Cladribine
- Action on Cladribine
- Outcome
- Relative Day from First Administration
- SAE (Yes/No).

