11.2 Severity of Adverse Events

Investigators should assess the severity/intensity of any AE as follows:

- Mild: The patient is aware of the event or symptom, but the event or symptom is easily tolerated.
- **Moderate:** The patient experiences sufficient discomfort to interfere with or reduce his or her usual level of activity.
- Severe: Significant impairment of functioning: the patient is unable to carry out usual activities.

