11.3 Causality Assessment of Adverse Events

Investigators must assess the causal relationship between AEs and study drug (including any other non-medicinal product, radiation therapy, etc.) considering temporal relationship between the AE onset and study drug administration, safety profile of study drug (known ADRs), the patient's condition (medical history, underlying disease), concomitant medication, and study procedures.

Related: Suspected to be reasonably related to any study medication.

Not related: Not suspected to be reasonably related to any study medication. A reasonable alternative explanation must be provided.

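### SAP 15.1.1 lets the worst severity and the worst relationship of a repeated AE come from different records, so the severity split of treatment-related TEAEs can show a severe reaction that was never recorded

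*SAP*

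**What the plan says.** SAP 15.1.1 gives a collapsing rule for a patient in whom one AE recurs: "the worst severity and the worst relationship to study drug will be tabulated". The overall frequency table that follows has separate rows for any TEAE, for treatment-related TEAEs (labelled as ADRs) and for any TEAE by severity. It also has a row that crosses the two attributes: "Treatment related TEAE by severity (Severe, Moderate, Mild".

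SAP 15.1 (Definitions) works at the level of the individual report: "ADRs will be those TEAEs reported in the eCRFs as related to study treatment or those AEs where such a relationship is missing".

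The Protocol collects both attributes event by event. Section 11.2: "Investigators should assess the severity/intensity of any AE as follows", with three levels. Section 11.3: "Investigators must assess the causal relationship between AEs and study drug", with two outcomes, related or not related.

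Event totals are planned as well: "The total number of TEAEs and rate (per patient-year of time on study) of TEAEs will be also reported". The all-AE listing in SAP 15.1.1 has a column for relationship but none for severity. The SAE listing in SAP 15.2.2 has both.

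**The concern.** The rule names two maxima and does not tie them to the same record. For rows that use one attribute this is harmless. For the row that crosses them, the literal procedure puts the highest severity and the strongest relationship on one line and then cross-tabulates. Suppose a patient has a mild headache judged related after the first treatment week and a severe headache judged unrelated in Month 10. That patient then appears as having a severe treatment-related headache. Because SAP 15.1 counts a missing relationship as related, a mild report with the relationship left blank has the same effect.

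ADRs are part of a stated secondary objective, and the first interim analysis is run mainly to evaluate safety (SAP 6.1). With two treatment courses and 24 to 30 months of follow-up, repeat reports of one term are foreseeable, although the documents give no frequency. At stake are the accuracy of the severity split and whether it can be reproduced from the SAP.

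**Working it through.** The plan states no figure on this point, so there is none to reproduce. The check applies two readings of the text to the same records.

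- **Reading A (literal 15.1.1):** take the maximum severity and the maximum relationship separately, join them, then cross-tabulate.
- **Reading B (ADR definition first):** keep only the reports that are related or have relationship missing, then take the worst severity among them.

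**Step 1. Worked patients, same AE reported twice**

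| Reports | Reading A | Reading B |
|---|---|---|
| mild related; severe unrelated | severe related | mild related |
| mild, relationship missing; severe unrelated | severe related | mild related |
| severe related; mild unrelated | severe related | severe related |
| mild related; severe related | severe related | severe related |

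**Step 2. All combinations.** Three severities and two relationships give 6 kinds of report, hence 6 × 6 = 36 ordered pairs. The readings differ only when exactly one report is related and the unrelated one is more severe. That is 3 severity pairs × 2 orders = 6 of 36. In 2 × 2 = 4 of these the unrelated report is severe, so Reading A creates a severe related entry that no record supports. In the other 2 it turns mild into moderate. This counts possible pairs, not their probability.

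**Step 3. What does not change.** In all 36 pairs both readings agree on whether the patient has any related TEAE. Any TEAE by severity uses the maximum over all reports under either reading. The number and rate of TEAEs count events and are not collapsed.

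**Step 4. Size among patients with repeats (assumed inputs).** Let ps be the chance that a report is severe, pr the chance that it is related, and k the number of reports, with all reports and both attributes independent. None of these inputs is in the documents.

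- Reading A: [1 − (1 − ps)^k] × [1 − (1 − pr)^k]
- Reading B: 1 − (1 − ps × pr)^k

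| ps | pr | k | Reading A | Reading B | Ratio |
|---|---|---|---|---|---|
| 0.05 | 0.20 | 2 | 0.0975 × 0.36 = 0.0351 | 1 − 0.99² = 0.0199 | 1.76 |
| 0.10 | 0.30 | 2 | 0.19 × 0.51 = 0.0969 | 1 − 0.97² = 0.0591 | 1.64 |
| 0.15 | 0.40 | 2 | 0.2775 × 0.64 = 0.1776 | 1 − 0.94² = 0.1164 | 1.53 |
| 0.10 | 0.30 | 3 | 0.271 × 0.657 = 0.1780 | 1 − 0.97³ = 0.0873 | 2.04 |

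With three reports, the same outer input pairs give ratios of 2.34 (5%/20%) and 1.79 (15%/40%). If repeat reports agree fully within a patient, the ratio is 1.

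**Step 5. Size across all patients with that AE (assumed inputs).** A patient with one report contributes 0.10 × 0.30 = 0.03 under both readings.

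- 5% have two reports: A = 0.95 × 0.03 + 0.05 × 0.0969 = 0.03335; B = 0.95 × 0.03 + 0.05 × 0.0591 = 0.03146; ratio 1.06.
- 20% have two reports: A = 0.80 × 0.03 + 0.20 × 0.0969 = 0.04338; B = 0.80 × 0.03 + 0.20 × 0.0591 = 0.03582; ratio 1.21.

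**The case against.** The strongest reply is that the SAP never says the two worst values are joined on one record. ADRs are defined report by report, the related row is labelled as ADRs, and both attributes are assessed per event. A programmer could reasonably select the ADR records first and then take the worst severity, which is the correct result. This stands as far as it goes: the artefact is permitted, not guaranteed. It does not remove the problem, because no section states the order of the two steps and the sentence in 15.1.1, taken at its word, gives the wrong count.

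It also stands that the analysis is descriptive, that there is one cohort and so no group comparison to distort, and that the error runs towards overstating harm. Repeat reports in one patient may largely agree, which would shrink the effect.

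A reader might infer more than the documents support:

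- That the severe ADR count is a headline result. The documents name ADRs as an outcome, but not severe ADRs.
- That the table would visibly contradict the listings. The all-AE listing has no severity column, so for non-serious events it cannot show a conflict. Only the SAE listing could.
- That treatment-related serious TEAEs are affected too. The rule covers severity and relationship and says nothing about seriousness.

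**Conclusion.** The concern holds in a limited form. SAP 15.1.1, read literally, can place a patient in the severe treatment-related row without any single report being both severe and related. The ADR definition in SAP 15.1 implies a different procedure, so the two sections need to be aligned.

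Only the severity split of treatment-related TEAEs is affected, and only for patients whose repeated reports of one AE disagree in the particular way shown in Step 2. The direction is towards overstated severity. The size cannot be derived from the documents. The ratios of about 1.5-1.8 for two reports rest on assumed proportions and on independence, and they apply only to patients with repeats. At table level the excess is much less, of the order of 6-21% in the illustration. These figures should not be read as a forecast for this study. The case for change is that the row cannot be reproduced from the SAP as written and that the correction is nearly free.

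**What to change.** Add to SAP 15.1.1, after the sentence on repeated events: 'For the row of treatment-related TEAEs by severity, only records that are themselves classed as related, or whose relationship is missing, are kept. The worst severity among those records is then tabulated for the patient.' The existing rule can stay for the rows that use severity or relationship alone.

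This wording keeps the SAP's convention that a missing relationship counts as related. It only stops such a record from borrowing the severity of an unrelated one.

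Optionally, add a severity column to the all-AE listing so that each entry in the row can be traced to a record.

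Cost: one SAP sentence, one subset step in the table program and, if wanted, one listing column. No new data are needed and no other table changes.
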